- Safety and Tolerability of reconstituted lyophilized lucinactant given as a bolus to patients with COVID-19.
- Change from baseline in OI at 12 hours post initiation of dosing. OI is defined as P_{aw}×FiO₂×100/PaO₂.

Secondary Efficacy Variables:

- Change from baseline through 24 hours post dosing initiation:
 - \circ FiO_{2:}
 - o PaO₂;
 - o SpO₂;
 - o OI;
 - o PaCO₂;
 - o ETCO₂;
 - P/F and or S/F ratios, defined as PaO₂ or SpO₂ divided by FiO₂;
 - Plateau pressure and peak inspiratory pressure (PIP) measured on the ventilator;
 - Ventilation Index (VI). VI is defined as $[RR \times (PIP PEEP) \times PaCO_2]/1000$;
 - o Lung compliance;
 - o Pressure-volume loops if ventilator technology permits.
- Through 30 days:
 - o Daily lung compliance (static) on ventilator;
 - Ventilator-free days;
 - o Days in the intensive care unit (ICU);
 - Days in the hospital;
 - o Incidence of all-cause mortality;
 - o Organ failure free days.

Safety Variables:

- All-cause mortality;
- Peri-dosing adverse events (desaturation, bradycardia, ET reflux, hypotension)
- AEs and serious AEs (SAEs). SAEs that are ongoing at Day 30 will be followed for an additional 30 days;
- Air leaks as AEs of special interest;
- Assessments of vital signs.

Study Population:

The study population will be comprised of adults 18-75 (inclusive) who are positive for SARS-CoV-2, are exhibiting symptoms of severe COVID-19 infection, who are intubated and are receiving mechanical ventilation in a critical care environment.

The objective of the pilot safety study is to evaluate the safety and feasibility of lucinactant administration in COVID-19 patients. A small number of patients should be sufficient to provide evidence that liquid lucinactant can be safely delivered as an intratracheal bolus. A total of up to 30 study subjects will be enrolled (see "Treatment Group" section).

Description of Sites:

Approximately 15 study sites in the United States and Argentina.

Description of Study Intervention:

Reconstituted lyophilized lucinactant will be given at a dose of 160 ml (30 mg TPL/ml), delivered as a liquid in the trachea through the endotracheal tube. Lyophilized lucinactant has the following four active ingredients:

- sinapultide (a synthetic peptide), consisting of amino acid residues lysine (K) and leucine (L), according to the sequence KLLLKLLLKLLLKLLLKKLLLK (KL₄);
- dipalmitoyl-phosphatidylcholine (DPPC);
- palmitoyloleoyl-phosphatidylglycerol, sodium salt (POPG, Na); and

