4.3 Justification for Dose

SRT has been proposed to treat ARDS in children and adults. SRT was initially successful in adult ARDS patients (5) and later in pediatric patients (39). These studies used a dose volume of 2–4 ml/kg.

Survanta® (25 mg phospholipid [PL]/ml) was administered to adult ARDS patients by endotracheal instillation (5). Three dose groups were studied: up to 8 doses of 100 mg PL/kg (4 ml/kg), up to 8 doses of 50 mg PL/kg (2 ml/kg), and up to 4 doses of 100 mg PL/kg (4 ml/kg). The

dosing strategies used were chosen on the basis of experience with animal models and the desire to use an incremental approach in applying this untested therapy to patients. The FiO₂ at 120 hours after treatment began was significantly decreased only for patients who received up to 4 doses of 100 mg PL/kg as compared with control patients (p =0.011). Mortality in the same group of patients was 18.8%, as compared with 43.8% in the control group (p =0.075). Intratracheal bolus instillation of Survanta was generally well tolerated, and no safety concerns were identified. Data did suggest that after 4 doses of 100 mg PL/kg, further doses were accompanied by greater reflux and transient increases in peak inspiratory pressure than were seen with initial doses and did not result in apparent improvement in measures of gas exchange.

Infasurf® (35 mg PL/ml) was administered to children, 1 week to 21 years of age, with ARDS by endotracheal instillation (39). Two doses of 80 ml/m² were administered to patients \geq 10 kg. Infants < 10 kg received 3 ml/kg (equivalent to the premature infant dose). The Infasurf group experienced a decrease in oxygenation index from 20 to 13.9 after 12 hours compared with the placebo group's decrease from 20.5 to 15.1 (p=.01). Mortality was significantly greater in the placebo group compared with the Infasurf group (36% vs 19.5%). No significant decrease in duration of ventilator therapy and ICU or hospital stay was observed. There were no differences in long-term complications.

Future studies in ARDS patients switched to a lower dose volume of approximately 1 mL/kg. This change in dose volume resulted in a failure of SRT in adults (40,41,42).

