7 STUDY INTERVENTION DISCONTINUATION AND PARTICIPANT DISCONTINUATION/WITHDRAWAL

7.1 Discontinuation of Study Intervention

Study treatment may be interrupted at any time as circumstances dictate (eg, peri-dosing event). In all cases, emergent care of the subject takes precedence over study treatment; however, it is important to complete SRT as soon as possible. If study treatment is interrupted or stopped, the reason for doing so must be recorded, especially in regard to peri-dosing events (bradycardia, desaturation, hypotension, pallor, gagging/regurgitation/vomiting).

Discontinuation from study treatment does not mean discontinuation from the study, and the remaining study procedures should be completed as indicated. If a clinically significant finding is identified after enrollment (including, but not limited to changes from baseline), the investigator or qualified designee will determine if any change in participant management is needed. Any new clinically relevant finding will be reported as an AE.

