8.3 Safety and Other Assessments

8.3.1.1 Concomitant Medications

Concomitant medications and therapies required for the general care of the subject are permitted, including remdesivir and off-label drugs. Other investigational agents or investigational medical devices should be avoided. Concomitant medications will be documented until the time the subject completes the Day 30, is discharged from the hospital, dies, or is transferred to another hospital. Dose, route, unit, frequency of administration, indication for administration, and dates of medication will be captured on the CRF.

8.3.1.2 *Tolerability of drug administration*

During dosing, the incidence of the following will be recorded:

- Oxygen desaturation
- Bradycardia
- Hypotension
- ET tube obstruction

In addition, information on (time, reason) and the incidence of dosing interruptions or dosing discontinuations will be collected.

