8.4.5 Adverse Event Reporting

All AEs are to be assessed in all subjects throughout Day 30 (from enrollment to study withdrawal or completion) and documented in the study eCRF. Each AE should be reported spontaneously or in response to general, non-directed discussion with the attending nurse or physician (eg, "has there been any change in subject status since the last assessment period?"). For each AE, the investigator should obtain all information required to complete the AE page of the eCRF, in accordance with eCRF completion guidelines (provided separately by Windtree).

All AEs, regardless of seriousness, severity, or relationship to study participation, must be recorded (using medical terminology) in the source document and on the AE page of the eCRF. Whenever possible, diagnoses should be given when signs and symptoms are due to a common etiology.

All AEs must be followed until resolution or until a stable clinical end-point is reached, or for at least 30 days after the subject's last day in the study if an AE is ongoing at the time the subject completes the study.

Documentation of AEs in the eCRF must include the following parameters; (1) duration (time of onset and resolution), (2) severity or grade, (3) outcome, (4) action taken, and (5) relationship to study drug. AEs will be coded using the Medical Dictionary for Regulatory Activities (MedDRA).

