#### **5.3.1 Peri-Dosing AEs**

The incidence of peri-dosing events (desaturation, bradycardia, ET reflux, hypotension, gagging/regurgitation/vomiting) will be summarized.

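### The peri-dosing event lists disagree: ET reflux is to be summarized but is missing from the protocol's dosing record, while ET tube obstruction is recorded but not named in the SAP summary

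*Protocol*

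**What the plan says.** The first primary endpoint in the Protocol 1.1 Summary is "Safety and Tolerability of reconstituted lyophilized lucinactant given as a bolus to patients with COVID-19". It names no component events. Peri-dosing events appear below it as safety variables: "Peri-dosing adverse events (desaturation, bradycardia, ET reflux, hypotension". The endpoint table in Protocol Section 3, the SAP Executive Summary and SAP 1.2.4 name the same four. SAP 1.2.4 adds that its listed safety measures are documented in the eCRF.

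The collection instruction is in Protocol 8.3.1.2 (tolerability of drug administration). It opens with "During dosing, the incidence of the following will be recorded" and lists oxygen desaturation, bradycardia, hypotension and "ET tube obstruction". It also asks for the time, reason and incidence of dosing interruptions and discontinuations.

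Protocol 7.1, on recording why treatment was interrupted or stopped, refers to "peri-dosing events (bradycardia, desaturation, hypotension, pallor, gagging/regurgitation/vomiting".

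SAP 5.3.1 defines the analysis: "The incidence of peri-dosing events (desaturation, bradycardia, ET reflux, hypotension, gagging/regurgitation/vomiting) will be summarized". The planned outputs are Table 5.1.1 (initial dose) and Table 5.1.2 (repeat doses).

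For adverse events in general, Protocol 8.4.5 says: "Each AE should be reported spontaneously or in response to general, non-directed discussion with the attending nurse or physician".

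**The concern.** In an uncontrolled study of an intratracheal bolus, the peri-dosing table is the most direct evidence on tolerability. Its rows can be read against one another only if the events were looked for in the same way. Protocol 8.3.1.2 gives desaturation, bradycardia and hypotension a named place in the dosing record. It gives ET reflux none, although the SAP plans to summarize it.

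Obstruction has the reverse problem. Sites are told to record it, but the SAP's peri-dosing summary does not name it. The protocol's own rationale (1.1 Summary) argues that the lower viscosity of the lyophilized product should reduce temporary airway obstruction, so readers will look for that result.

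DMC reviews (Protocol 10.1.6.2) may give particular attention to peri-dosing events, so an uneven list would also affect oversight during the study. Bedside observations that nobody was asked to record are hard to recover later.

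**Working it through.** The plan states no event rate, capture rate or sample size calculation, so there is no figure to reproduce. The check is a comparison of the lists.

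| Event | Endpoint lists (Protocol 1.1 and 3; SAP Executive Summary and 1.2.4) | Dosing record (Protocol 8.3.1.2) | Interruption reasons (Protocol 7.1) | Analysis (SAP 5.3.1) |
|---|---|---|---|---|
| Desaturation | yes | yes | yes | yes |
| Bradycardia | yes | yes | yes | yes |
| Hypotension | yes | yes | yes | yes |
| ET reflux | yes | no | no | yes |
| ET tube obstruction | no | yes | no | no |
| Gagging/regurgitation/vomiting | no | no | yes | yes |
| Pallor | no | no | yes | no |

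Reading across:

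- In all four versions: desaturation, bradycardia, hypotension.
- In the analysis but not in the dosing record: ET reflux and gagging/regurgitation/vomiting.
- In the dosing record but not in the analysis: ET tube obstruction.
- In Protocol 7.1 only: pallor.

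Next, the routes by which each mismatched event can reach a table.

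1. ET reflux. SAP 1.2.4 places it in the eCRF, but Protocol 8.3.1.2 does not list it. Under the protocol it can enter as an adverse event (8.4.5, by spontaneous or non-directed report) or as the reason for an interruption (7.1 and 8.3.1.2). The second route covers only episodes that interrupted or stopped a dose. Protocol 7.1 names regurgitation rather than ET reflux, and SAP 5.3.1 treats these as different items.
2. ET tube obstruction. If entered as an adverse event, it falls under the other treatment-emergent events in SAP 5.3.3 and appears in Tables 5.3.1 to 5.3.5. If it stays only on the dosing record, no listed table names it. The documents do not say which applies.

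The effect of incomplete capture can be illustrated, but only with assumed inputs. Let n be the number treated, p the true share of subjects with reflux and s the share of those cases recorded. The expected recorded count is n × p × s, and the chance that none is recorded is (1 − p × s)^n. Take p = 20% as an assumption, with n = 30 (Protocol 9.2) or n = 20 (SAP 2.2.3):

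| s (assumed) | Expected count, n = 30 | Chance of none, n = 30 | Expected count, n = 20 | Chance of none, n = 20 |
|---|---|---|---|---|
| 1.00 | 6.0 | 0.1% | 4.0 | 1.2% |
| 0.75 | 4.5 | 0.8% | 3.0 | 3.9% |
| 0.50 | 3.0 | 4.2% | 2.0 | 12.2% |
| 0.25 | 1.5 | 21.5% | 1.0 | 35.8% |

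For example, with n = 30 and s = 0.50: 30 × 0.20 × 0.50 = 3.0, and (1 − 0.10)^30 = 4.2%. The range runs from no loss to a loss of three quarters. Nothing in the documents says where in it the study would fall.

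**The case against.** The strongest reply is that SAP 1.2.4 already makes ET reflux an eCRF item. The eCRF and its completion guidelines are not among the documents, and Protocol 8.3.1.2 does not say its list is exhaustive. Dosing is given by the investigator or an approved person (6.4), and the investigator stays for the first 10 minutes afterwards (6.1.2). All adverse events must be recorded (8.4.5). An observed reflux may well be captured whatever the list says. This stands, and it limits the point to a contradiction and a risk.

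A reader might infer four stronger things that the documents do not support:

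- That reflux is under-counted. This would need the eCRF content or a capture rate, and neither is given.
- That obstruction is collected and then lost. It lacks a named place in SAP 5.3.1, but as an adverse event it would reach the treatment-emergent tables. The titles of Tables 5.1.1 and 5.1.2 do not close the list either.
- That reflux is a primary endpoint event. The primary endpoint names no components; reflux is a safety variable that supports it.
- That the dose rationale makes reflux a known problem of this regimen. Protocol 4.3 says "further doses were accompanied by greater reflux and transient increases in peak inspiratory pressure", but this concerns another surfactant and doses given after four doses of 100 mg PL/kg. This trial allows one initial dose and up to three retreatments, 1 + 3 = 4 in all, so the cited increase lies beyond its maximum number of doses.

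What remains is that the protocol, which sites follow at the bedside, and the SAP disagree on which events are collected. SAP 1.2.4 does not settle that; it is one side of the disagreement.

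**Conclusion.** The inconsistency is established from the text: four versions of the list, with three events common to all. Two items that SAP 5.3.1 will summarize are absent from the protocol's dosing record, and one item in the dosing record is absent from that summary.

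The consequence is a risk of uneven capture, so that the reflux row of Tables 5.1.1 and 5.1.2 may not be comparable with the rows for desaturation, bradycardia and hypotension. This assumes that sites work from Protocol 8.3.1.2 and that the dosing form mirrors it. If the form already follows SAP 1.2.4, little or nothing is lost for reflux, but the documents still need aligning and obstruction still lacks a named row. The size of any under-count cannot be determined from the documents. The point should be fixed because it bears on the evidence for a primary endpoint and the remedy is cheap.

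**What to change.** Use one peri-dosing list in the Protocol 1.1 Summary, Protocol Sections 3, 7.1 and 8.3.1.2, the SAP Executive Summary, and SAP 1.2.4 and 5.3.1. It should cover at least desaturation, bradycardia, hypotension, ET reflux, gagging/regurgitation/vomiting and ET tube obstruction. Keep gagging/regurgitation/vomiting as its own row, because SAP 5.3.1 separates it from reflux. For pallor, either add it or state that it serves only as a reason for interruption.

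Collect each event as a prompted yes/no for the initial dose and for every retreatment, and give each a row in Tables 5.1.1 and 5.1.2. State in Protocol 8.3.1.2 and SAP 5.3.1 whether events on the dosing record are also entered as adverse events, so that it is clear which events appear in both sets of tables.

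The cost is a few tick-boxes on the dosing eCRF and aligned wording in two documents. The tolerability table may show more events, which should be read as fuller capture. No dose or treatment rule changes.

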8.4 Adverse Events and Serious Adverse Events

8.4.1 Definition of Adverse Events

An adverse event (AE) is defined as any untoward medical occurrence associated with the use of an intervention, whether or not considered intervention related. An AE can therefore be any unfavorable and unintended sign (including an abnormal laboratory finding), symptom, or disease temporally associated with the use of an investigational product [21 CFR 312.32(a), ICH E6(R2)].

8.4.2 Definition of Serious Adverse Events

An AE or suspected adverse reaction is considered "serious" if, in the view of either the investigator or sponsor, it results in any of the following outcomes: death, a life-threatening adverse event, inpatient hospitalization or prolongation of existing hospitalization, a persistent or significant incapacity or substantial disruption of the ability to conduct normal life functions, or a congenital anomaly/birth defect. Important medical events that may not result in death, be life-threatening, or require hospitalization may be considered serious when, based upon appropriate medical judgment, they may jeopardize the participant and may require medical or surgical intervention to prevent one of the outcomes listed in this definition. Examples of such medical events include allergic bronchospasm requiring intensive treatment in an emergency room or at home, blood dyscrasias or convulsions that do not result in inpatient hospitalization.

8.4.3 Classification of an Adverse Event

8.4.3.1 Severity of Event

The severity of an AE is assessed by the PI using the following definitions:

- **Mild** Events require minimal or no treatment and do not interfere with the subject's daily activities.
- **Moderate** Events result in a low level of inconvenience or concern with the therapeutic measures. Moderate events may cause some interference with functioning.
- Severe Events interrupt a subject's usual activity level and may require systemic drug therapy or other treatment. Severe events may be potentially life-threatening or incapacitating. Of note, the term "severe" does not necessarily equate to "serious."

8.4.3.2 Relationship to Study Intervention

All AEs must have their relationship to study intervention assessed by the PI, based on temporal relationship and his/her clinical judgment. The degree of certainty about causality will be graded using the categories below. In a clinical trial, the study product must always be suspect.

- Related There is clear evidence to suggest a causal relationship, and other possible contributing factors can be ruled out. The clinical event, including an abnormal laboratory test result, occurs in a plausible time relationship to study intervention administration, follows a known response pattern to the study intervention, and cannot be explained by concurrent disease or other drugs or chemicals. An AE that is determined to be due to the subject's underlying disease state or is common for this patient population generally should not be considered related.
- Possibly Related There is some evidence to suggest a causal relationship (eg, the event occurred within a reasonable time after administration of the trial medication) and/or follows a known response pattern to the study drug. However, other factors may have contributed to the event (eg, the participant's clinical condition, other concomitant events). Although an AE may rate only as "possibly related" soon after discovery, it can be flagged as requiring more information and later be upgraded to "related," if appropriate. An AE that is determined to be due to the subject's underlying disease state or is common for this patient population generally should not be considered possibly related.
- Unlikely Related A clinical event, including an abnormal laboratory test result, whose temporal relationship to study intervention administration makes a causal relationship improbable (eg, the event did not occur within a reasonable time after administration of the study intervention) and in which other drugs or chemicals or underlying disease provides plausible explanations (eg, the subject's clinical condition, other concomitant treatments).
- **Not Related** The AE is completely independent of study intervention administration, and/or evidence exists that the event is definitely related to another etiology. There should be an alternative, definitive etiology documented by the clinician.]

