2.4 Risk/Benefit Assessment

2.4.1 Known Potential Risks

Risks for this study must be considered within the context of treating adults with COVID-19, which carries with it substantial risk of morbidity and mortality. Intratracheal instillation of surfactant into the lung requires endotracheal intubation, often with concomitant positive pressure MV. However, patients in this trial will have been intubated to treat their underlying condition. MV is associated with morbidities such as ventilator-associated lung injury and volutrauma/barotrauma resulting in air leak syndromes such as pneumothorax and/or pulmonary interstitial emphysema (PIE). Surfactant instilled intratracheally has been associated with peridosing events such as transient hypoxemia, bradycardia, and hypotension. These are usually not severe, are transient, and typically resolve within 30 minutes.

Studies in adults with ARDS administered lucinactant using bronchopulmonary surfactant lavage of each segment of the lungs to attempt to remove alveolar debris and effectively deposit functional surfactant. Safety results show that this procedure was generally safe and well tolerated; however, this procedure was more invasive than other delivery methods and required more time and skill to complete dosing and may have contributed to the increased treatment-emergent AE in the lucinactant-treated subjects. A total of 44 of 110 lucinactant patients (40%) and 14 of 42 standard of care patients (33%) experienced an SAE. A total of 15 of 88 lucinactant patients (17%) in KL4-ARDS-04 had an SAE that was considered to be related to study treatment (patients receiving

standard of care had all AEs and SAEs defined as not study-treatment related). A total of 28 deaths were observed in the ARDS studies. In the KL4-ARDS-04 Study, all-cause mortality at the end of Day 28 was numerically, but not statistically significantly, higher in lucinactant Group B.2 (24%) compared with lucinactant Group B.1 and SOC (14% in each).

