- 4.9.1 Efficacy Analysis – Plateau Pressure and Peak Inspiratory Pressure (PIP) through 24 Hours – Modified Intent-to-Treat Population
- 4.9.2 Efficacy Analysis – Plateau Pressure and Peak Inspiratory Pressure (PIP) through 24 Hours – Intent-to-Treat Population
- 4.10.1 Efficacy Analysis – Ventilation Index (VI) through 24 Hours – Modified Intent-to-Treat Population
- 4.10.2 Efficacy Analysis – Ventilation Index (VI) through 24 Hours – Intent-to-Treat Population
- 4.11.1 Efficacy Analysis – Lung Compliance (Dynamic) through 24 Hours – Modified Intent-to-Treat Population
- 4.11.2 Efficacy Analysis – Lung Compliance (Dynamic) through 24 Hours – Intent-to-Treat Population
- 4.12.1 Efficacy Analysis – Daily Lung Compliance (Static) on Ventilator – Modified Intent-to-Treat Population
- 4.12.2 Efficacy Analysis – Daily Lung Compliance (Static) on Ventilator – Intent-to-Treat Population
- 4.13.1 Efficacy Analysis – Ventilator Free Days – Modified Intent-to-Treat Population
- 4.13.2 Efficacy Analysis – Ventilator Free Days – Intent-to-Treat Population
- 4.14.1 Efficacy Analysis – Days in the Intensive Care Unit (ICU) – Modified Intent-to-Treat Population
- 4.14.2 Efficacy Analysis – Days in the Intensive Care Unit (ICU) – Intent-to-Treat Population
- 4.15.1 Efficacy Analysis – Days in the Hospital – Modified Intent-to-Treat Population
- 4.15.2 Efficacy Analysis – Days in the Hospital – Intent-to-Treat Population
- 4.16.1 Efficacy Analysis – Incidence of All-Cause Mortality – Modified Intent-to-Treat Population
- 4.16.2 Efficacy Analysis – Incidence of All-Cause Mortality – Intent-to-Treat Population
- 4.17.1 Efficacy Analysis – Organ Failure Free Days – Modified Intent-to-Treat Population
- 4.17.2 Efficacy Analysis – Organ Failure Free Days – Intent-to-Treat Population
- 5.1.1 Peri-Dosing Adverse Events – Initial Dose – Safety Population
- 5.1.2 Peri-Dosing Adverse Events – Repeat Doses – Safety Population
- 5.2 Air Leaks – Safety Population
- 5.3.1 Treatment-Emergent Adverse Events by System Organ Class and Preferred Term – Safety Population
- 5.3.2 Treatment-Emergent Adverse Events by System Organ Class and Preferred Term by Severity – Safety Population
- 5.3.3 Treatment-Emergent Adverse Events by System Organ Class and Preferred Term by Relationship to Study Treatment – Safety Population
- 5.3.4 Treatment-Emergent Adverse Events by System Organ Class and Preferred Term by Severity and Relationship to Study Treatment – Safety Population

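### The causality definitions steer investigators away from Related or Possibly Related when an event is merely common in this population, which biases the relationship tables downward by an unknown amount

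*Protocol*

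**What the plan says.** Protocol 8.4.3.2 has the PI grade every AE as Related, Possibly Related, Unlikely Related or Not Related, from timing and clinical judgement. It opens with a principle: "In a clinical trial, the study product must always be suspect".

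The Related definition ends by saying that an event due to the subject's underlying disease, or one that "is common for this patient population generally should not be considered related", stays out of that category. Possibly Related ends the same way: such an event, or one that "is common for this patient population generally should not be considered possibly related", stays out. In both sentences the two grounds are joined by *or*.

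Protocol 2.4.1 names the known effects of this route of administration: "Surfactant instilled intratracheally has been associated with peridosing events such as transient hypoxemia, bradycardia, and hypotension".

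The SAP's list of tables includes TEAEs (Table 5.3.3) and SAEs (Table 5.4.3) by "System Organ Class and Preferred Term by Relationship to Study Treatment". Table 5.3.4 crosses severity with relationship.

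**The concern.** How often an event occurs in ventilated COVID-19 patients says nothing about whether this dose caused it in this subject. A drug whose known effects resemble the disease will produce events that are also common in the disease, and the clause acts on those events.

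Safety and tolerability is a primary endpoint (Protocol 1.1; SAP 1.2.2), and there is no comparison group (Protocol 9.1). In a two-arm trial a shared tendency to under-attribute would leave the all-cause contrast between arms to correct it. Here no such contrast exists, so an error in the grading rule passes straight into the relationship tables.

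**Working it through.** The plan states no figure on this point, so the check is a reading of the definitions against each other and against the tables they feed.

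**1. What triggers the exclusion.** The first ground, underlying disease, is a finding about the individual subject. The second, commonness, is a property of the population. Because of the *or*, the second is enough without the first.

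**2. A test case.** Take a desaturation during instillation in a subject who met the entry criteria, so with P/F below 300 (Protocol 5.1).

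| Category | What the definition needs | Does the event fit? |
|---|---|---|
| Related | Plausible timing, known pattern, other causes ruled out, not explicable by concurrent disease | No. Concurrent disease could explain it, so it fails before the commonness clause is reached |
| Possibly Related | Reasonable timing and/or an event that "follows a known response pattern to the study drug. However, other factors may have contributed to the event" | Yes on every substantive criterion, but the commonness clause then discourages it |
| Unlikely Related | An event "whose temporal relationship to study intervention administration makes a causal relationship improbable", and another plausible explanation | No. The second half is met, but the timing is not improbable |
| Not Related | Complete independence from dosing and/or evidence of a definite other etiology, documented | No |

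Only the commonness clause keeps the event out of Possibly Related, and neither lower category admits it on its own terms. The investigator must override the clause or misapply another definition. The clause matters mainly in Possibly Related, since Related already excludes anything concurrent disease can explain.

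**3. Which events are exposed.**
- *Desaturation or hypoxemia*: associated with instilled surfactant in 2.4.1, and hypoxemia is built into the population by the P/F criterion. Both halves come from the documents.
- *Bradycardia and hypotension*: also associated with instilled surfactant in 2.4.1, but the documents do not say how common they are here. Protocol 5.1 allows vasopressors at entry, which hints at hypotension. It also requires a mean blood pressure of at least 65 mmHg, and 5.2 excludes multiple-dose vasopressors.
- *Air leak*: 2.4.1 assigns it to ventilation: "MV is associated with morbidities such as ventilator-associated lung injury and volutrauma/barotrauma" is the start of the sentence that leads to it. Only the heading of SAP 5.3.2 ties it to surfactant.

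**4. Where the grade goes.** It enters Tables 5.3.3, 5.3.4 and 5.4.3, the investigator's assessment in each SAE report (Protocol 8.4.6), and the SAP 5.3.3 summary of TEAEs with a remote or stronger relationship. It does not enter the peri-dosing tables (5.1.1, 5.1.2), air leaks (5.2), all TEAEs (5.3.1) or all SAEs (5.4.1). The DMC review in Protocol 10.1.6.2 has no relationship filter.

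**5. Direction and size.** The clause only moves events out of the two positive categories, so the bias is downward. Its size depends on the share of events that investigators move, which the documents do not provide.

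**The case against.** The strongest defence is that the clause says *generally* and leaves the call to the PI's judgement. ICU patients have many events unrelated to any study drug, and some guard against labelling all of them possibly related is reasonable. A PI who sees a desaturation during instillation has good textual grounds for Possibly Related despite the clause. A downgraded event stays in Table 5.3.3 under another category. All AEs are recorded regardless of relationship (Protocol 8.4.4).

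Most of this stands, and it rules out three stronger readings a reader might draw:

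- *That the clause removes these events from the safety record.* It does not. It shifts the grade of some of them.
- *That investigator attribution is the only causal information in the trial.* It is the only recorded causal judgement, but timing evidence is collected without a relationship filter: events during dosing, the time and reason for interruptions and discontinuations (Protocol 8.3.1.2), and separate peri-dosing tables for initial and repeat doses. Attribution carries more weight for the bradycardia and desaturation after the peri-dosing period that SAP 5.3.2 also summarises, where timing says less.
- *That air leak is an established effect of the drug being hidden.* The risk section attributes it to ventilation, and it has its own unfiltered table.

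The defence does not rescue the clause. The underlying-disease ground already guards against over-attribution and asks the right question. Commonness adds only a default that the rest of the section contradicts.

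**Conclusion.** The point holds as a defect in the grading definitions and should be corrected. Protocol 8.4.3.2 contradicts itself, and the relationship assessments and Tables 5.3.3, 5.3.4 and 5.4.3 are biased downward as a result. This is well supported for desaturation or hypoxemia. For bradycardia and hypotension it rests on the assumption that investigators would regard them as common here. All-cause counts and DMC review are unaffected.

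No size can be given. A reader might carry over the related-SAE rate in Protocol 2.4.1, 15/88 = 17%, expect 30 × 15/88 = 5.1 subjects with a related SAE among 30, and infer that the clause could bring this to 0. The documents do not support that. The rate comes from bronchopulmonary lavage, which the protocol calls more invasive than other delivery methods. It counts SAEs of unstated type, whereas 2.4.1 describes peri-dosing events as mostly transient and not severe. Zero would require every such event to be regraded, which *generally* does not imply, and no other share can be justified from the text.

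**What to change.** In Protocol 8.4.3.2, delete the commonness alternative from the closing sentences of both Related and Possibly Related. Keep the ground about events determined to be due to the subject's underlying disease, and require the alternative cause to be documented, as Not Related already asks. Timing and known response pattern then decide the grade. The deletion has its main effect in Possibly Related; making it in both keeps the definitions consistent.

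In the same revision, align the SAP 5.3.3 summary of remotely related TEAEs with the four protocol categories, since a remote relationship is not one of them.

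The cost is a short amendment and a training note to sites. Sample size, schedule and treatment do not change. Related-AE counts may look somewhat less favourable.
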